9.4.3 ANALYSIS OF THE SECONDARY ENDPOINT(S)

The secondary analysis (Aim 2) comparing changes in Mini-AHA among the three treatment groups will use a generalized linear mixed model with repeated measures to model the change in Mini-AHA at the End of Treatment and 6 mos. Post-Treatment; the same set of subgroup analyses are proposed for this endpoint. For the secondary analysis, the sequentially rejective hypothesis testing procedure must first reject the series of null hypotheses of no difference at 6 months post-treatment before testing for differences at 4 weeks post-treatment.

9.4.4 EXPLORATORY ANALYSES

The exploratory analyses (Aim 3) for GMFM-66 and Bayley-4 Cognitive subtests will follow the model and sequence of hypothesis tests described for the secondary endpoint. For missing secondary and exploratory endpoints, the mixed effects model naturally accounts for missing data and has been shown to be more powerful than either the last observation carried forward or multiple imputation approaches.

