Measures of child development for Exploratory Aim 3: Gross Motor Function Measure (GMFM-66) and the Bayley-4 Cognitive subtest. The GMFM-66⁷ measures gross motor function in children with cerebral palsy (5 mos - 16 yrs). 66 items are scored each on a 4-point scale and grouped into 5 domains (lying and rolling; sitting; crawling and kneeling; standing; and walking, running, and jumping); an overall GMFM Total Score also is computed. The GMFM-66 is considered valid and sensitive to changes in children with neuromotor impairment. We will use the Total Score in the exploratory analyses relating treatment group to gross motor development.

(One surgical intervention study¹²⁷ established a minimal clinically meaningful outcome on the GMFM-66 for older children as a gain of 2.7 points, although a gain of only 0.7 was deemed clinically useful for some patients. We will work with the Parent Council and clinicians to determine whether these (or other) thresholds might be suitable to consider for interpreting findings about GMFM-66 for children with PAIS.)

The Bayley Scales of Infant and Toddler Development-4 (Bayley-4) is the most widely used tool to assess infants (3 - 42 mos). It underwent major revision and re-norming in 2019, including children with disabilities.¹⁰⁷ It yields subtest scores for Fine Motor, Gross Motor, Language, Self-help, and Cognition and an overall Developmental Quotient (DQ). For Exploratory Aim 3, we primarily plan to use the Cognitive subtest (scores from 0 – 19, mean of 10, SD=3 pts) to consider whether one or both doses of I-ACQUIRE, compared to U&CT, are associated with significant gains in Cognition. We predict, based on theory, that the High Dose group will show larger mean cognitive gains than the children in the Moderate Dose or U&CT groups, and that likely these become detectable by the 6 mos. Post-Treatment Assessment. Our reasoning is if I-ACQUIRE produces large gains in UE skills (the primary and secondary efficacy outcomes), then treated children will be able to increase their successful interactions with their environment which, in turn, could improve their learning and problem-solving skills and lead to higher Bayley-4 Cognitive scores. Other subtests may also show benefits that will be considered in exploratory analyses.

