9 STATISTICAL CONSIDERATIONS

9.1 STATISTICAL HYPOTHESES

1. Primary Aim: Determine the efficacy of I-ACQUIRE at 2 dosage levels compared to U&CT to increase upper extremity skills on the hemiparetic side. The primary efficacy outcome is a gain and retention of ≥ 7 new skills on the Emerging Behaviors Scale (EBS) at the end of the 4-wk treatment and 6 mos. later.

Hypothesis 1A: The 3 groups will differ significantly in the proportion of infants meeting primary efficacy criteria.
Hypothesis 1B: Both the Moderate Dose and High Dose I-ACQUIRE groups will have significantly higher proportions of infants meeting the primary efficacy criteria compared to U&CT.

Hypothesis 1C: The High Dose compared to Moderate Dose I-ACQUIRE group will have a significantly higher proportion of infants meeting the primary efficacy criteria.

Additional sensitivity analyses using repeated EBS scores (from 0 – 30) will explore specific aspects of treatment outcome and maintenance (e.g., differential magnitude of EBS changes across treatment groups) in relationship to predictor variables (e.g., stroke CNS damage coded from MRI scans, family engagement levels).

2. Secondary Aim: Determine the efficacy of I-ACQUIRE at 2 dosage levels compared to U&CT to improve use of the hemiparetic upper extremity in bimanual activities. The secondary efficacy outcome is the Mini Assisting Hand Assessment score at the end of 4-wk treatment and 6 mos. later.

Hypothesis 2A: The 3 groups will differ significantly in mean Mini AHAs at end of treatment and 6 mos later.

Hypothesis 2B: Both the Moderate Dose and High Dose I-ACQUIRE groups will have significantly higher mean Mini AHAs compared to U&CT at the end of treatment and 6 mos later.

Hypothesis 2C: High Dose compared to Moderate Dose I-ACQUIRE will have significantly higher Mini AHAs at end of treatment and 6 mos later.

3. Exploratory Aim: Explore the association between I-ACQUIRE treatment at Moderate and High Doses and gross motor development and cognition (i.e., cross-domain effects of treatment).

3A. Evidence-informed prediction for motor development: Both Moderate and High Doses of I-ACQUIRE will have higher mean gains in Gross Motor skills compared to U&CT at end of treatment and 6 mos later.

3B. Theory-informed prediction about cognition: High Dose I-ACQUIRE will be associated with larger mean gains in Cognition (Bayley-4) than Moderate Dose I-ACQUIRE and U&CT at 6 mos post-treatment.

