9.4 STATISTICAL ANALYSES

9.4.1 GENERAL APPROACH

Randomization. Randomization will take place centrally via a web-based central randomization system (described above) developed by the National Data Management Center (NDMC).

Multiplicity and Control of Type I Error. Inflation of the type-I error through multiple hypothesis testing is controlled using a sequentially rejective multiple test procedures approach to address repeated testing of pairwise comparison and hypothesis tests of multiple primary, secondary, and exploratory endpoints. This method, which generalizes the approach for closed testing procedures including Bonferroni-Holm, fixed sequence, fallback, and gatekeeping procedures, defines the sequence in which hypotheses and families of hypotheses are tested and sequentially allocates the local type I error rate to guarantee strong control of the familywise error rate (i.e. the probability of incorrectly rejecting at least one true null hypothesis given any configuration of true or false null hypotheses). This approach also provides corresponding methods for correctly specifying the adjusted p-values and confidence intervals with a minimum of $1-\alpha$ coverage. The primary and secondary aims will each test a sequence of null hypotheses comparing 1) whether a difference exists among the three treatment groups, 2) whether Moderate and High Dose I-ACQUIRE each differ from U&CT, and 3) whether Moderate Dose I-ACQUIRE is different from High Dose I-ACQUIRE at a local familywise two-sided type I error rate of 5%. A given hypothesis may only be tested if the previous hypothesis has been rejected.

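### The test order borrowed from the Mini AHA makes the High v Moderate half of cognition prediction 3B wait for a Moderate v U&CT difference that 3B does not predict

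*Protocol*

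**What the plan says.** Protocol section 9.1, prediction 3B: "High Dose I-ACQUIRE will be associated with larger mean gains in Cognition (Bayley-4) than Moderate Dose I-ACQUIRE and U&CT at 6 mos post-treatment". Section 8.2 repeats it: "the High Dose group will show larger mean cognitive gains than the children in the Moderate Dose or U&CT groups". Neither statement predicts a difference between Moderate and U&CT on cognition. Prediction 3A, for gross motor skills, does put both doses above U&CT.

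Section 9.4.4 gives GMFM-66 and Bayley-4 Cognition one shared rule: they "will follow the model and sequence of hypothesis tests described for the secondary endpoint". Section 9.4.1 sets that sequence in three steps:

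1. "whether a difference exists among the three treatment groups"
2. "whether Moderate and High Dose I-ACQUIRE each differ from U&CT"
3. Moderate v High, with a two-sided local familywise rate of 5%.

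The gate is strict: "A given hypothesis may only be tested if the previous hypothesis has been rejected". Section 9.4.3 adds the order of visits: the procedure "must first reject the series of null hypotheses of no difference at 6 months post-treatment before testing for differences at 4 weeks post-treatment".

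**The concern.** The order suits an endpoint where both doses are expected to beat U&CT, as 3A expects for GMFM-66. It does not suit 3B. For cognition, a contrast that 3B does not predict (Moderate v U&CT) stands ahead of one that it does (High v Moderate). If the Moderate Dose has little effect on cognition at 6 months, 3B can be true and High v Moderate will usually never be formally tested. At stake is the dose half of the cognition prediction, not the High v U&CT half.

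**Working it through.** **Inputs.** 80 per group (section 4.1); two-sided 5% (section 9.4.1); a planning difference of 5 units with SD 10, that is 0.5 SD, for secondary and exploratory endpoints, single time point and unadjusted (section 9.2); Bayley-4 Cognitive SD of 3 points (section 8.2), so 0.5 SD = 1.5 points, 0.8 SD = 2.4 and 1.0 SD = 3.0 if the SD of change is also 3; up to 15% loss (section 9.2), leaving 0.85 × 80 = 68 per group.

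**The plan's own figure.** Pairwise power = Φ(d/√(2/n) − 1.96). With d = 0.5 and n = 80: 0.5/0.158 = 3.16, and Φ(1.20) = 88.5%. With n = 68: 0.5/0.171 = 2.92, and Φ(0.96) = 83%. The stated power of at least 80% reproduces. It is for one pair tested alone and takes no account of the gate.

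**The gate.** High v Moderate is reached only if the three-group test, Moderate v U&CT and High v U&CT all reject. The chance of reaching it therefore cannot exceed the power of Moderate v U&CT. If Moderate equals U&CT, that ceiling is 5% for any High effect.

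**Simulation** (three normal group means, three-group test at 5%, pairwise two-sided 5% tests, at least 400,000 replicates, 80 per group). The last two columns give the chance of reaching and rejecting High v Moderate.

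| Moderate v U&CT (SD) | High v U&CT (SD) | As written | Directly after three-group test |
|---|---|---|---|
| 0 | 0.5 | 2.6% | 86% |
| 0 | 0.8 | 4.9% | 99.9% |
| 0.125 (a quarter) | 0.5 | 4.0% | 64% |
| 0.2 (a quarter) | 0.8 | 22% | 97% |
| 0.25 (half) | 0.5 | 5.6% | 34% |
| 0.4 (half) | 0.8 | 46% | 72% |
| 0.5 (half) | 1.0 | 77% | 89% |

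With 68 per group, Moderate equal to U&CT and High +0.5 SD, the figures are 2.1% v 79%.

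**High v U&CT.** This is a step-2 test. With Moderate equal to U&CT and High +0.5 SD, it is reached and rejected in 86% of trials with step 2 at 5% for each pair, and in 81% with Holm.

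**Error rate of the alternative.** With three groups, a three-group test at 5% followed by unordered pairwise tests at 5% is a closed procedure: if exactly one pair is equal, only that one true null can be falsely rejected. Simulated familywise error at one visit was 5.0% with all groups equal, with only Moderate equal to U&CT, and with only High equal to Moderate.

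**The visit gate.** Take High +0.8 SD and Moderate equal to U&CT at 6 months, no differences at End of Treatment, and a correlation between visits of 0 to 0.7 (assumed). If End of Treatment opens once the two High contrasts reject, the two-visit familywise error is 8.8-9.7%; at zero correlation it is about 1 − 0.95 × 0.95 = 9.75%. If all three 6-month pairs must reject first, it is 5.0%.

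**The case against.** Several points on the other side are sound.

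- A reader might infer that 3B predicts an effect of the High Dose alone, so that it is almost never testable when true. The documents do not support this. 3B ranks High above the other two groups and leaves Moderate v U&CT open. Section 8.2 also says the Cognitive subtest will be used to ask whether either dose, or both, gains over U&CT, so Moderate v U&CT is a legitimate cognition question. Where Moderate has half of a large High effect, High v Moderate is rejected in 46-77% of trials as written.
- A reader might infer that the cognition question gets no answer at all. It does get one: High v U&CT is tested in step 2. The model's High v Moderate estimate and interval also remain available for description.
- The gate asks for a two-sided difference, not for Moderate to be better than U&CT.
- Section 9.4.1 does not spell out whether step 3 needs both step-2 rejections or only one. Both is the natural reading of a rule that requires the previous hypothesis to be rejected. If one were enough, High v Moderate would be reached and rejected in about 82% of trials with Moderate equal to U&CT and High +0.5 SD, and the problem would largely go. A SAP may settle this.
- Aim 3 is exploratory, and section 3 makes it conditional on efficacy for the primary and/or secondary outcome.

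These points narrow the finding without removing it. The protocol fixes the order itself and includes exploratory endpoints in its multiplicity control. The written order did worse for High v Moderate in every scenario above.

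**Conclusion.** The mismatch is real but limited. As naturally read, the order in section 9.4.4 ties the High v Moderate half of 3B to a Moderate v U&CT rejection that 3B does not predict. The cost ranges from severe (2.6% v 86%) when Moderate is no better than U&CT to modest (77% v 89%) when Moderate has half of a 1.0 SD High effect. The range rests on an assumed Moderate effect, equal SDs, 80 evaluable children per arm, one time point and unadjusted tests. High v U&CT is not blocked. No primary or secondary conclusion depends on this, so the severity is minor.

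**What to change.** In section 9.4.4, give Bayley-4 Cognition its own rule at 6 months: run the three-group test at 5%; if it rejects, test High v U&CT, High v Moderate and Moderate v U&CT each at two-sided 5%, with no order among them. This rejects everything the written order would reject, and sometimes more, with familywise error of 5% at that visit.

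Keep the existing rule that the whole 6-month series, all three pairs, must be rejected before End of Treatment is tested. Opening End of Treatment after only the two High contrasts would raise the two-visit familywise error to about 9-10%.

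GMFM-66 can keep its present order, which fits 3A. The cost is one or two sentences in section 9.4.4 and matching wording in the SAP where it repeats the order. No data or participants are added.

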9.4.5 SAFETY ANALYSES

All reportable AEs and SAEs will be summarized by Meddra term and body system in terms of frequency of the event, number of subjects having the event, severity, and relatedness to the study treatment. The proportion of subjects experiencing each of these events will be provided in the closed report by treatment arm with two-sided 95% CIs and unadjusted relative risks. Fisher's exact tests will be used to assess treatment group differences in the rates of serious adverse events.

9.4.6 TABULATION OF INDIVIDUAL PARTICIPANT DATA

Coded individual participant data will be examined and presented in data presentations in ways that fully protect privacy and anonymity.

10 SUPPORTING DOCUMENTATION AND OPERATIONAL CONSIDERATIONS

10.1 REGULATORY, ETHICAL, AND STUDY OVERSIGHT CONSIDERATIONS

10.1.1 INFORMED CONSENT/ PARENTAL PERMISSION PROCESS

10.1.1.1 CONSENT/ASSENT AND OTHER INFORMATIONAL DOCUMENTS PROVIDED TO PARTICIPANTS

Consent forms describing in detail the study intervention, study procedures, and risks are given to the parent of the participant and written documentation of informed consent/ parental permission is required prior to starting intervention. The following consent materials are submitted with this protocol:

Informed Consent Document/ Parental Permission

In accordance with ICH-GCP Consolidated Guidelines, a CIRB-approved informed consent is required for all participants prior to participating in this study. The informed consent is obtained by either the clinical site PI or other members of the study team who are qualified to perform this task and are designated to do so on the Delegation of Authority Log (DOA).

10.1.1.2 CONSENT PROCEDURES AND DOCUMENTATION

Informed consent/ parental permission for each child to participate is a process that is initiated prior to the child participating in any study procedures. Consent (permission) forms will be approved by StrokeNet's Central Institutional Review Board (CIRB). The participant's parent/guardian will be asked to read and review the document at the first study visit. The investigator will explain the research study to the parent/guardian and answer any questions that may arise. This verbal explanation will be provided in terms suited to the parent/guardian's comprehension and explain the purposes, procedures, and potential risks of the study and their rights as parents of a research participant. Participant's parents/guardians will have the opportunity to carefully review the written consent form and ask questions prior to signing. The participant's parents/guardians will have the opportunity to discuss the study with their family or surrogates and have a minimum of 24 hours prior to the implementation of any study procedures after enrollment to think about all study processes. The participants in this study will be children below the age of eight, so their assent is not required. Consent is considered to be ongoing throughout the study period.

While the participant's parent/guardian will sign the informed consent/parental permission document at enrollment, they will verbally be reminded of all planned study processes at the first Baseline Assessment and be asked to confirm their willingness to participate prior to any study procedures starting. Parents and guardians will be informed at enrollment and at this second point of consent validation that participation is voluntary and that they may withdraw from the study at any time, without prejudice. A copy of the informed consent/parental permission document will be given to the parents/guardians for their records. The informed consent process/parental permission will be conducted and documented in the source document (including the date), and the form signed, before the participant undergoes any study-specific procedures. A phone/fax alternative for the consent procedures and documentation will be available if the participant's parents/guardians cannot come in person to a recruitment site office. (see description of procedure in I-ACQUIRE Manual of Procedures (MOP)) The participant's rights and welfare will be protected by emphasizing to parents that the quality of their child's medical care will not be adversely affected if they decline to participate in this study.

10.1.2 STUDY DISCONTINUATION AND CLOSURE

This study may be temporarily suspended or prematurely terminated if there is sufficient reasonable cause. Written notification, documenting the reason for study suspension or termination, will be provided by the suspending or terminating party to study participants, investigator, and funding agency. If the study is prematurely terminated or suspended, the Principal Investigator (PI) will promptly inform study participants, the Institutional Review Board (IRB), and sponsor and will provide the reason(s) for the termination or suspension. Study participants will be contacted, as applicable, and be informed of changes to study visit schedule.

Circumstances that may warrant termination or suspension include, but are not limited to:

- Determination of unexpected, significant, or unacceptable risk to participants
- Demonstration of efficacy that would warrant stopping
- Insufficient compliance to protocol requirements
- Data that are not sufficiently complete and/or evaluable
- Determination that the primary endpoint has been met
- Determination of futility

Study may resume once concerns about safety, protocol compliance, and data quality are addressed, and satisfy the sponsor.

10.1.3 CONFIDENTIALITY AND PRIVACY

Participant confidentiality and privacy is strictly held in trust by the participating investigators, their staff, and the sponsor(s) and their interventions. This confidentiality is extended to cover testing of biological samples and genetic tests in addition to the clinical information relating to participants. Therefore, the study protocol, documentation, data, and all other information generated will be held in strict confidence. No information concerning the study, or the data will be released to any unauthorized third party without prior written approval of the sponsor.

All research activities will be conducted in as private a setting as possible.

The study monitor, other authorized representatives of the sponsor, representatives of the CIRB, or regulatory agencies may inspect all documents and records required to be maintained by the investigator, including but not limited to, medical records (office, clinic, or hospital) and pharmacy records for the participants in this study. The clinical study site will permit access to such records.

The study participant's contact information will be securely stored at each clinical site for internal use during the study. At the end of the study, all records will continue to be kept in a secure location for as long a period as dictated by the reviewing IRB, institutional policies, or sponsor requirements.

Study participant research data, which is for purposes of statistical analysis and scientific reporting, will be transmitted to and stored at the Data Coordinating Center. This will not include the participant's contact or identifying information. Rather, individual participants and their research data will be identified by a unique study identification number.

10.1.4 FUTURE USE OF STORED SPECIMENS AND DATA

Data will be stored for possible future use, such as a longitudinal follow-up of the participating children and their families or for new coding methodologies of the stored assessment data or for new exploratory data analyses. In the event that there would be future use, we would contact parents who indicated they would be willing to be contacted when they signed the original consent document. Any future use would be subject to CIRB review and approval in advance of proceeding.

Samples collected for genetic study will be stored if consent is granted for the future study of the samples. Any future use would be subject to CIRB review and approval in advance of proceeding.

The I-ACQUIRE principal investigators (Drs. [name] and [name]) have responsibility for ensuring protection of data confidentiality. All of the protections in place for The I-ACQUIRE Study extend to the addition of the new biomarker data. The lab at Yale University will produce the DNA polymorphism results, associated only with subject I.D. codes. The lab team sends these results to the Assessment Center for entry into the I-ACQUIRE centralized database that adheres to strict guidelines protecting subject confidentiality. If a sample is deemed inadequate by the lab, then the Assessment Center will notify the local site so that a second set of swabs can be obtained during the next assessment visit and re-submitted for that study participant. (Only the local sites maintain the names and contact information associated with subject I.D. code.) Any new investigators joining the study must be approved and adhere to all local and central IRB guidelines.

Only the collaborating lab at Yale has access to the samples directly after these are mailed to the lab by the local site. In the event that something happens that requires the samples to transfer to another lab setting, the Multiple PIs and Executive Steering Committee of the I-ACQUIRE Study will vet the location and provide supportive data that standards for patient confidentiality, high lab standards, and safe and secure storage are met. We will immediately notify the CIRB and provide needed information if there is a need for a change in plans related to access, lab analysis, and storage.

Patient samples will be stored by study I.D. code, compliant with HIPAA regulations.

Specimen and Data Storage

The I-ACQUIRE principal investigators (Drs. [name] and [name] and Local Site PIs) have access to subject identities. All proposed data analyses linking biological markers to other aspects of a subject's dataset do not require having subject identities.

The DNA samples will be stored at the research laboratory at Yale University.

Samples will be stored in locked freezers that are in a locked laboratory accessible only to authorized personnel. Lab personnel adhere to strict guidelines about who can assess secured specimens linked to the parent I-ACQUIRE Study.

The samples will be destroyed 10 years after the completion of the primary planned data analyses for the I-ACQUIRE Study.

We have requested separate parent permission to store any unused DNA for future studies. We advise parents that deidentified DNA samples may be shared with NIH biorepositories for future research uses that go beyond the original purposes for the biomarker study linked to the parent I-ACQUIRE Study.

Specimen and Data Distribution

An agreement will require the investigators state the purpose of the proposed research, show that the research has been approved by the appropriate IRB, affirm that the investigators guarantee that they will not attempt to de-identify the data by any means, and understand that there will be no secondary distribution of the samples. We also will require investigators outside of the protocol to acknowledge in any publications and presentation that the I-ACQUIRE Study was the source of the samples.

No specimens be made available to commercial organizations.

Associated data will be provided with the specimen that the child sustained a perinatal arterial ischemic stroke.

Policy on Withdrawal of Specimens/Data

We allow parents granting permission for collecting the DNA samples from their child to withdraw and ask that no biomarker data about their child be used or stored. We do inform parents, however, that if they choose to withdraw permission after excess DNA from their child already was transferred to the deidentified storage, this will not be possible. We do let parents know that we would be able to delete the biomarker data in the dataset for their own child. We tell parents there will no negative consequences if they change their mind to have their participate.

